We hypothesise that earlier detection of a major anomaly could alter women's preferences for continuing a pregnancy and so will construct our model to simulate the impact on the pregnancy termination rate and the number of babies born with a major anomaly. An increased risk of miscarriage from invasive testing following a false positive early screen will also be considered. Equally important is the impact on parents. The psychological sequelae of terminating a pregnancy for a major anomaly are significant and any additional burden should be reflected (10, 11, 55, 56). Furthermore, the potential for false positive results with early screening and the associated anxiety and morbidity from additional invasive testing must also be considered. In contrast, earlier anomaly detection and intervention may avert some of the distress, and may avoid the additional pressures that parents feel to reach a decision about their pregnancy before the 24-week legal termination limit (55). Also, and should a termination be chosen, an earlier procedure may expose women to less physical harm than a later procedure. We plan to explore the likely net impact of all of these consequences upon maternal and parental utility during the pregnancy.

We foresee a need to compare variants of protocols (with different anatomical specifications / screening modalities and personnel / interventional pathways) and expect to operationalise these as alternative comparators within a decision tree model covering each of the three trimesters to birth. Within each trimester, the model will be structured for any anomaly screening results, related prevalence and sensitivity/specificity and intervention pathways, and will be populated with data on associated event

probabilities, costs, and parental and infant payoffs. Separate outcomes will be presented using the decision tree and will include births with a major anomaly, and maternal and parental utility during the pregnancy (expressed as quality adjusted life years (QALYs)). At this stage, we anticipate a paucity of data on the false positive rate (and hence specificity) of tests. The statistics will also vary by anomaly. Where data are not forthcoming we will seek expert opinion using a structured elicitation technique (e.g. SHELF) (57).

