If the hypotheses above are correct, the implications of first trimester anomaly screening will extend beyond the pregnancy. For example, there may be long term cost-savings for the NHS and social services as well as a reduction in the parental burden of caring for a child born with a major anomaly. However, the notion that these benefits are realised through an increase in the number of pregnancies being terminated is ethically challenging. Indeed, the likely preferences of society for such a program are unclear. This in turn raises questions about the use of conventional cost-utility analyses whereby results are interpreted within the context of society's valuation of a QALY (54, 58). Although our primary approach will take the form of a cost-consequence analysis, we will also calculate incremental cost-effectiveness ratios, but would emphasise that in the light of the sensitivities discussed above, that these should be interpreted with caution.

Protocol alternatives and input parameters for the model will be informed by WPs 1, 2, and 3 as well as by supplementary literature searching and expert elicitation. We will utilise the planned national survey to elicit information on pregnancy termination rates with and without first trimester anomaly screening and will interrogate the Department of Health's termination statistics. Cost data will be sourced from administrative datasets, hospital finance departments, and the published literature. Model parameters will be entered as distributions and the resulting simulated costs and outcomes of each alternative will be compared to rule out dominated and extended dominated protocols. Incremental cost-effectiveness ratios (and/or net health/monetary benefit) will be computed for the remaining protocols and a VoI analysis conducted. These analyses will be conducted for various outcomes (including the number of births with an anomaly, and maternal quality adjusted life years) so as to make clear the social value judgements that arise when outcomes for different affected parties are considered. As a secondary analysis, we will also perform these works using the long-term cost and QALY framework, if viable.

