Our intention will be to use the individual cost-effectiveness outcomes modelled (for example cost per live births with an anomaly averted or cost per maternal QALYs gained) in separate VoI analyses, which will also provide evidence regarding any recommendation about subsequent research. The cost-consequence approach to the economic analysis will allow the potential implications of the policy for the various affected parties (the babies, parents, and wider society) to be fully quantified and reported separately.

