4.2. Value of Information (VoI) analysis

Using the model's facility for probabilistic sensitivity analysis, we will calculate the expected value of perfect information (EVPI) and partial perfect information (EVPPI) and if either suggests value from future research, we will explore the expected value of sample information (EVSI), expected costs, and the expected net gain of sampling (ENGS) for various trial designs and sample sizes.

VoI analysis is complicated by the inability to calculate a single meaningful incremental cost per QALY gained from the screening intervention. We will, therefore, conduct these from the outcome perspectives of the mother, both parents, and if appropriate, from society too. The exact specification will be determined prior to analysis, but may, for example, in the case of the mother and parental perspectives, lead to the outcome being dichotomised into 'desirable' or 'undesirable', where a desirable outcome is one where a fetus is either carried to term or terminated in accordance with the wishes of the parent(s). Thus, the driver for 'undesirable' outcomes will be a function only of the false positive and negative rate of the screening test, thereby avoiding any social value judgements associated with the decision itself. The EVSI will then be interpreted as the expected gain in 'desirable' outcomes from additional information yielded from a trial. The cost and EVSI from alternative trial designs can then be compared in stepwise manner, excluding dominated and extended dominated options.

WP 5: Determining the final study design

We will draw together the findings and recommendations from the project, and, if appropriate, outline the design of plausible prospective studies. The Vol analysis will be rerun to predict the expected net gain of sampling (ENGs) of these. Where appropriate, this will include identifying the most efficient sample size for such studies, the range of sample sizes yielding a positive ENGs, and comparisons with the sample size yielded from a traditional power calculation.

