If a study is deemed efficient, we will develop the relevant parameters. Possible designs include a prospective cohort screening study with ascertainment of outcomes; here we would explore whether it is acceptable to women and caregivers not to reveal those anomalies that are associated with a high false positive rate or thought to resolve spontaneously in a large number of cases, e.g. small exomphalos or megacystis of <15mm diameter (14, 59).

It would also be possible to undertake a randomised trial with women randomised to having or not having the first trimester anomaly screening test. All women in the screened arm who have a positive first-level result would then have further detailed assessment.

We will also consider the possibility of randomising at hospital level, e.g. using a cluster or stepped wedge RCT. Finally, we would also consider the potential use of an adaptive trial design. The team includes a senior statistician and leading trialists ([name], [name], [name], [name]), who have extensive experience of different methodological approaches.

Details of candidate study designs will be defined in specifically designed workshops with the PPV group. Particular aspects will be acceptability of:

- different study designs;
- reporting only major anatomical landmarks and blinded research elements for more detailed assessment;
- non-disclosure of suspected (but unconfirmed) anomalies;
- consent procedure.

The impact of declining or accepting screening for chromosomal abnormalities, including cell-free DNA screening, will be assessed in the context of anomaly screening. This is important as some anomalies (e.g. exomphalos, megacystis, holoprosencephaly) are strongly associated with trisomy 13 and 18 (60, 61). Hence, detecting such anomalies may itself increase the chances of a pregnancy being affected by such a trisomy.

WP 6: Analysis of UK-based data currently held by the National Congenital Anomalies Disease Registry

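### The example parental VoI outcome is defined by parents' wishes but said to depend only on false positive and false negative rates, which does not follow

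*Protocol*

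**What the plan says.** Section 4.2 of the Protocol (in section 6, WP 4) explains that a single cost per QALY is not meaningful here, so the VoI analysis will be run from several perspectives. For the mother and parents it gives one possible form, introduced with "The exact specification will be determined prior to analysis, but may, for example". In that form the outcome is split in two, and the desirable half is defined by the parents' wishes ("a desirable outcome is one where a fetus is either carried to term or terminated in accordance with the wishes of the parent(s"). The next sentence draws the consequence that "the driver for 'undesirable' outcomes will be a function only of the false positive and negative rate of the screening test", and gives the reason that value judgements about the decision itself are thereby avoided. It continues: "The EVSI will then be interpreted as the expected gain in 'desirable' outcomes from additional information yielded from a trial".

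Section 4.1 builds the model on the hypothesis that "earlier detection of a major anomaly could alter women's preferences for continuing a pregnancy", simulates the termination rate, and plans to use the national survey to "elicit information on pregnancy termination rates with and without first trimester anomaly screening". It also plans separate VoI analyses on other outcomes, for example "cost per live births with an anomaly averted or cost per maternal QALYs gained". Sections 7 and 9 expect the second-trimester scan to be kept.

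**The concern.** The definition asks how the pregnancy ended relative to what the parents wanted. The stated driver asks only how often the test is wrong. These are different quantities. An error changes whether the ending was wished for only if it changes what the parents do. That depends on whether a false positive is later refuted, whether a miss is picked up at the second scan, and whether the parents would have terminated had they known.

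An outcome that depends only on the two error rates leaves all three out. On the outcome side of this analysis, removing uncertainty about any of them could then have no value, although altered preference is the model's own hypothesis. The EVSI would be reported as a gain in outcomes matching the parents' wishes while measuring something else. WP 5 reruns the VoI analysis to judge candidate studies and their efficient sample size, so the definition could affect the project's final recommendation.

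**Working it through.** **Logic.** The plan states no figure for this outcome, so there is nothing to reproduce. The two sentences of section 4.2 can be set side by side on individual cases:

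| Case | Test error? | Ending against the parents' wishes? |
|---|---|---|
| False positive, refuted later, carried to term as wished | Yes | No |
| False positive, not refuted, pregnancy terminated | Yes | Yes, judged against the true fetal status; no, if read literally |
| Anomaly missed at first scan, found at second | Yes (first scan) | No; the parents still choose |
| Missed at both scans, parents would have continued | Yes | No |
| Missed at both scans, parents would have terminated | Yes | Yes |

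All five are errors of the first scan. At most two defeat the parents' wishes. Moving from one column to the other requires probabilities that the word 'only' excludes.

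**Illustration per 10,000 pregnancies.**

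Inputs from the Protocol:
- Prevalence 203.35 per 10,000 (section 3; non-chromosomal anomalies).
- First-trimester sensitivity 46.10%, stated to be 53.47% of all antenatally diagnosed abnormalities (WP 1, question 1.1; major anomalies). Overall antenatal detection is therefore about 46.10/53.47 = 86.2%.

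Assumed inputs, for which the Protocol gives no value:
- False positive rate 0.5% (range 0.1% to 1%).
- *w*, the probability of termination if the anomaly is detected: 0.2 to 0.8.
- *t*, the probability that a false positive is not refuted and ends in termination: 0 to 0.2.
- Miscarriage after invasive testing is ignored.

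Errors at the end of the prenatal pathway:
- Misses = 203.35 × (1 − 0.862) ≈ 28.0
- False positives = (10,000 − 203.35) × 0.005 ≈ 49.0
- Total ≈ 77, the same for every *w* and *t*.

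Outcomes against the parents' wishes = *w* × misses + *t* × false positives:
- Lowest: 0.2 × 28.0 + 0 × 49.0 = 5.6
- Highest: 0.8 × 28.0 + 0.2 × 49.0 = 22.4 + 9.8 = 32.2

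The wish-based count varies nearly 6-fold while the error count does not move. At a false positive rate of 0.1% the comparison is 37.8 errors against 5.6 to 24.4. At 1% it is 126.0 against 5.6 to 42.0.

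**Could the ranking of screening protocols reverse?** Suppose a more sensitive protocol reaches 55.46% (the upper confidence limit) while the false positive rate rises from an assumed 0.5% to 0.8%.
- Extra first-scan detections: 203.35 × (0.5546 − 0.4610) = 19.0.
- First-scan misses at 46.10%: 203.35 × 0.539 = 109.6, of which 28.0/109.6 = 25.6% remain missed antenatally. If the extra detections resemble the other first-scan misses (an assumption), about 19.0 × 0.256 = 4.9 end-of-pathway misses are avoided.
- Extra false positives: 9,796.65 × 0.003 = 29.4.
- Net by error count: 4.9 − 29.4 = −24.5.
- Net by wishes: *w* × 4.9 − *t* × 29.4. The best case is 0.8 × 4.9 = +3.9. At *w* = 0.2 and *t* = 0.1 it is −2.0, and at *t* = 0.2 it is −4.9.

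The sign may or may not differ, depending on inputs that the Protocol does not give.

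**The case against.** The strongest reply is that nothing has been fixed. The dichotomy is an illustration, and the exact specification is to be set before analysis. That stands, and it limits the point to what happens if the example is adopted as written. It is still the only form spelled out for the mother and parental perspectives, and its consequence is stated without qualification.

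Second, a reader might infer that every error is scored as one undesirable outcome, with false positives and misses weighted equally. The text does not say so. It can also mean that errors are the only cause of undesirable outcomes. On that reading 'only' is still wrong, because turning errors into outcomes needs confirmation, second-scan detection and uptake.

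Third, a reader might conclude that the whole VoI analysis ignores termination uptake. It does not: the analyses on anomaly births and maternal QALYs can respond to it, and so can costs.

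Fourth, a reader might infer that the error-based outcome is bound to rank screening protocols wrongly. Counting only first-scan misses would suggest that, but the second scan is retained and the result then goes either way.

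Finally, the sentence that "All women in the screened arm who have a positive first-level result would then have further detailed assessment" comes from WP 5 and describes one candidate randomised trial. It shows that refuting false positives is envisaged, not that the WP 4 model already includes it.

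**Conclusion.** The two sentences in section 4.2 are inconsistent. A wish-based outcome is not a function of the error rates alone. If the example is adopted as written, termination uptake, confirmation and second-scan detection carry no EVPPI on the outcome side of this one analysis, and the EVSI cannot be interpreted as a gain in outcomes matching the parents' wishes. That conclusion follows from the word 'only' and needs no numerical assumption.

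The illustration (about 77 errors against about 6 to 32 outcomes the parents did not want, per 10,000) rests on an assumed false positive rate, uptake and share of false positives terminated. It also combines a prevalence for non-chromosomal anomalies with a sensitivity for major anomalies. It shows the direction of the effect, not its size. A reversed ranking of screening protocols is possible but not shown. The matter is worth correcting now because the specification is still open.

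**What to change.** Before the specification is set, reconcile the two sentences in one of two ways.

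(a) Keep the wish-based definition, but state it against what the parents would have chosen knowing the true fetal status. Delete 'only'. Compute undesirable outcomes as FP × P(not refuted and terminated) + end-of-pathway FN × P(termination if detected). Enter these probabilities as distributions in the probabilistic sensitivity analysis and include them in the EVPPI. They describe what parents do and place no value on the decision, so the stated aim of avoiding value judgements is kept.

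(b) Rename the outcome 'screening error', and do not interpret the EVSI as a gain in outcomes that match the parents' wishes.

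Option (b) costs only rewording. Option (a) is cheap in structure: the planned decision tree already follows test results and intervention pathways by trimester, and termination rates are to be collected. Its real cost is that the probability of termination after an unrefuted false positive is not specifically planned for collection. It would need expert elicitation, for which section 4.1 already provides.

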15.1 Scientific publications

We anticipate a series of publications that address the different aims of the project. First, we anticipate that we will publish a series of systematic reviews as described in WP 1. Second, we will publish systematic reviews of management pathways that are not currently informed by an up-to-date systematic review. Third, we will publish a health economic analysis of the case for implementing a program of detailed early screening for fetal anomalies, using different levels of uncertainty in screening performance. Fourth, we will publish a value of information analysis, which informs the economic case for performing the trial. Finally, if applicable, we will publish an outline for an RCT, including an overview of the rationale for the approach developed.

15.2 Dissemination through our Patient and Public Voice group

We anticipate wide dissemination of the study through the PPV group that has committee to undertake this through the relevant charity websites, social media and local meetings.

15.3 Scientific presentations

The PI and co-PIs are all very active in local, national and international meetings where ultrasound screening is an area of interest. In addition, some of the applicants organise national and international conferences, courses and meetings. Hence, there would be a huge potential exposure of the work from this project to audiences in the UK and internationally.

The PI and co-PIs also have close links with the organisations that inform and lead clinical practice in the UK. For example [name] is an advisor to the UK National Fetal Anomaly Screening Programme; [name] is a senior member of the British Medical Ultrasound Society and author of several key prenatal screening policy documents; [name] was the senior author of the chapter on Prenatal Screening in the Chief Medical Officer's 2014 Annual Report; [name] and [name] are current members of the RCOG Research Committee and [name] is a Council member of the RCOG; [name] is the Director of the Fetal Medicine Foundation; [name] is the chair of the Clinical Standards Committee of the International Society of Ultrasound in Obstetrics and Gynecology (ISUOG), and co-author of the international first trimester screening guidelines of ISUOG; while [name] is the Honorary Secretary of the same organisation. Hence, although high quality publications of original research are a key element of the dissemination policy, the applicants are well placed to ensure wider dissemination through multiple channels.

16. Plan of investigation and timetable:

| Work Package | 2018 | 2019 | | | | 2020 | | | | 2021 | | | | 2022 | | | | |
|--|------|------|----|----|----|-------------|-------------|-------------|-------------|------|----|----|----|------|----|----|----|--|
| | Q4 | Q1 | Q2 | Q3 | Q4 | Q1 | Q2 | Q3 | Q4 | Q1 | Q2 | Q3 | Q4 | Q1 | Q2 | Q3 | Q4 | |
| WP1: Systematic Reviews & Meta-Analyses | | | | | | | | | | | | | | | | | | |
| WP2: Nationwide Survey of Current Screening Environment | | | | | | | | | | | | | | | | | | |
| WP3: Delphi Consensus Procedure | | | | | | | | | | | | | | | | | | |
| WP4: Economic Model Development | | | | | | | | | | | | | | | | | | |
| WP5: Deliberations and Consensus on Possible Future Trial Design | | | | | | | | | | | | | | | | | | |
| WP5: Shaping the Final Study & Protocol Drafting | | | | | | | | | | | | | | | | | | |
| WP6: Collaboration with NCARDS | | | | | | permissions | permissions | permissions | permissions | | | | | | | | | |
| WP7: Acceptability of the early anomaly scan | | | | | | | | | | | | | | | | | | |
| Project Write-Up & Dissemination of Results | | | | | | | | | | | | | | | | | | |

Work disrupted due to COVID-19

17. Project management

The Study Steering Group (SSG) will include all co-applicants. Additional meetings will be held by the PPV group; and hospital management group, and feed into the groups. The chair of each will also be represented on the SSG. The day to day management of the study will be the remit of the coordinating centre at Oxford (AP, Research associate, ORA, HC), while alternate month face-to-face meetings will be facilitated with the health economics group at Cambridge. Finally, the independent advisory committee will oversee the smooth running of the study and provide expertise on ensuring progress of research and dissemination.

All applicants are highly engaged in the proposal. Collaborative management of the project when active will be through (i) teleconferences (TC) every 2 weeks, (ii) face to face meetings every quarter. In addition, consensus meetings will be held according to the timetable. Written minutes will be circulated by email following both TCs and face to face meetings, and will include a summary of action points. Each subsequent TC or face to face meeting will assess progress on the action points from the preceding meeting. Progress towards the overall aims of the project will be assessed in relation to the Gantt chart, and achievement of milestones.

[figure not shown]

Fig. 1: Study governance structure.

18. Approval by ethics committees

Most of the work included in the present proposal involves analysis of existing studies, and application of health economic analyses to their output. The study also includes workshops and surveys of women who would be the target population for future studies. Ethics approval to conduct workshops and surveys with women to discuss their attitudes to screening will be obtained prior to the start date.

19. Patient and Public Involvement

The PPV group will be one of the channels that allows us to engage women and the public. However, while we are clearly aware of the constituency of parents who have had anomalies detected during pregnancy, we are also very aware that there are many other constituencies, and that different groups will have different perspectives and priorities. We regard it as essential that all perspectives are included in our assessment of the views of women and the public, and consultation with other groups may also occur.

20. Expertise and justification of support required

